8.1.1 Dose Discontinuation

Study treatment should be permanently discontinued for the following:

- Any Grade 2 drug-related uveitis, eye pain or blurred vision that does not respond to topical therapy and does not improve to Grade 1 severity within the re-treatment period OR requires systemic treatment
- Any Grade 3 non-skin, drug-related adverse event lasting > 7 days, or recurs with the following exceptions for laboratory abnormalities, diarrhea, colitis, neurologic toxicity, drug-related

uveitis, pneumonitis, bronchospasm, hypersensitivity reactions, infusion reactions, and endocrinopathies:

- Grade 3 drug-related diarrhea, colitis, neurologic toxicity, uveitis, pneumonitis, bronchospasm, hypersensitivity reaction, or infusion reaction of any duration requires discontinuation
- Grade 3 drug-related endocrinopathies, adequately controlled with only physiologic hormone replacement do not require discontinuation. Adrenal insufficiency requires discontinuation regardless of control with hormone replacement.
- Grade 3 drug-related laboratory abnormalities do not require treatment discontinuation except:
 - ◆ Grade 3 drug-related thrombocytopenia > 7 days or associated with bleeding requires discontinuation
 - ◆ Any drug-related liver function test (LFT) abnormality that meets the following criteria require discontinuation:
 - Grade ≥ 3 drug-related AST, ALT or Total Bilirubin requires discontinuation*
 - Concurrent AST or ALT > 3 x ULN and total bilirubin > 2x ULN

* In most cases of Grade 3 AST or ALT elevation, study drug(s) will be permanently discontinued. If the investigator determines a possible favorable benefit/risk ratio that warrants continuation of study drug(s), a discussion between the investigator and the BMS Medical Monitor/designee must occur.

- Any Grade 4 drug-related adverse event or laboratory abnormality (including but not limited to creatinine, AST, ALT, or Total Bilirubin), except for the following events which do not require discontinuation:
 - Grade 4 neutropenia ≤ 7 days
 - Grade 4 lymphopenia or leukopenia or asymptomatic amylase or lipase
 - Isolated Grade 4 electrolyte imbalances/abnormalities that are not associated with clinical sequelae and are corrected with supplementation/appropriate management within 72 hours of their onset
 - Grade 4 drug-related endocrinopathy adverse events, such as, hyper- or hypothyroidism, or glucose intolerance, which resolve or are adequately controlled with physiologic hormone replacement (corticosteroids, thyroid hormones) or glucose-controlling agents, respectively, may not require discontinuation after discussion with and approval from the BMS Medical Monitor.

- Any event that leads to delay in dosing lasting > 8 weeks during Cycle 1- 2, and >10 weeks in cycle 3 or later for Cohorts 2-4, and >10 weeks for Cohort 1, from the previous dose requires discontinuation, with the following exceptions:
 - Dosing delays to allow for prolonged steroid tapers to manage drug-related adverse events are allowed.
 - Dosing delays lasting longer than the number of weeks allowed for the respective cohorts that occur for non-drug-related reasons may be allowed if approved by the BMS medical monitor.

Prior to re-initiating treatment in a participant with a dosing delay lasting > 8 weeks for Cohorts 2 through 4, or >10 weeks for Cohort 1, the BMS medical monitor must be consulted and provide written approval for participants with expected clinical benefit as per investigator assessment. Tumor assessments should continue as per protocol even if dosing is delayed. Periodic study visits to assess safety and laboratory studies should also continue every 6 weeks or more frequently if clinically indicated during such dosing delays.

Any adverse event, laboratory abnormality, or intercurrent illness which, in the judgment of the Investigator, presents a substantial clinical risk to the participant with continued nivolumab dosing.

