6.2 Exclusion Criteria

1) Medical Conditions

- a) Women with a positive pregnancy test at enrollment or prior to administration of study medication
- b) Any active or recent history of a known or suspected autoimmune disease or recent history of a syndrome that required systemic corticosteroids (> 10 mg daily prednisone equivalent) or immunosuppressive medications except for syndromes which would not be expected to recur in the absence of an external trigger. Participants with vitiligo or type I diabetes mellitus or residual hypothyroidism due to autoimmune thyroiditis only requiring hormone replacement are permitted to enroll.
- c) Any condition requiring systemic treatment with corticosteroids (> 10 mg daily prednisone equivalents) or other immunosuppressive medications within 14 days prior to first dose of

study drug. Inhaled steroids and adrenal replacement steroid doses > 10 mg daily prednisone equivalents are permitted in the absence of active autoimmune disease.

- d) Uncontrolled adrenal insufficiency.
- e) Prior malignancy active within the previous 3 years except for locally curable cancers that have been apparently cured, such as basal or squamous cell skin cancer, superficial bladder cancer, or carcinoma in situ of the prostate, cervix, or breast.
- f) Known history of testing positive for human immunodeficiency virus (HIV) or known acquired immunodeficiency syndrome (AIDS) as per local requirements.
- g) Any positive test for hepatitis B or hepatitis C virus indicating acute or chronic infection.
- h) Known medical condition (eg, a condition associated with diarrhea or acute diverticulitis) that, in the investigator's opinion, would increase the risk associated with study participation or study drug administration or interfere with the interpretation of safety results.
- i) Major surgery (eg, nephrectomy) less than 28 days prior to the first dose of study drug.

2) Prior/Concomitant Therapy

- a) Prior systemic treatment in the metastatic setting with VEGF or VEGF receptor targeted therapy (including, but not limited to, sunitinib, pazopanib, axitinib, tivozanib, bevacizumab, cabozantinib, and lenvatinib)
- b) Prior treatment with an anti-PD-1, anti-PD-L1, anti-PD-L2, anti-CD137, or anti-CTLA-4 antibody, or any other antibody or drug specifically targeting T-cell co-stimulation or checkpoint pathways. This includes the utilization of these agents in the neo-adjuvant or adjuvant setting.

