8.1.2 Criteria to Resume Treatment

Missed doses of nivolumab and/or ipilimumab should be administered as soon as the participant meets criteria to resume treatment. If a dose has been missed, the participant should not wait until the next scheduled dosing date.

Participants may resume treatment with study drug when the drug-related AE(s) resolve to Grade ≤ 1 or baseline value, with the following exceptions:

- Participants may resume treatment in the presence of Grade 2 fatigue
- Participants who have not experienced a Grade 3 drug-related skin AE may resume treatment in the presence of Grade 2 skin toxicity
- For participants with Grade 2 AST, ALT and/or Total Bilirubin Abnormalities, dosing may resume when laboratory values return to baseline and management with corticosteroids, if needed, is complete.
- Participants with combined Grade 2 AST/ALT AND total bilirubin values meeting discontinuation parameters ([Section 8.1.1](#)) should have treatment permanently discontinued.
- Drug-related pulmonary toxicity, diarrhea or colitis must have resolved to baseline before treatment is resumed. Participants with persistent Grade 1 pneumonitis after completion of a steroid taper over at least 1 month may be eligible for retreatment if discussed with and approved by BMS Medical Monitor.
- Participants with drug-related endocrinopathies adequately controlled with only physiologic hormone replacement may resume treatment after consultation with the BMS Medical Monitor.
- Adrenal insufficiency requires discontinuation regardless of control with hormone replacement.

If treatment is delayed > 8weeks for Cohorts 2 through 4, or >10 weeks for Cohort 1, the participant must be permanently discontinued from study therapy, except as specified in [Section 8.1.1](#).

For participants in Cohort 1, during Cycles 1 and 2, both nivolumab and ipilimumab must be resumed on the same day. For participants in Cohort 2 to 4, all four doses of nivolumab combined with ipilimumab must be given prior to beginning nivolumab monotherapy (Cycle 3 and beyond). Participants in any cohort, who discontinue combination therapy early due to an adverse event, may be eligible to receive nivolumab monotherapy (480 mg every 4 weeks), contingent upon discussion with, and approval by the Medical Monitor.

If the participant is unable to receive either combination therapy or nivolumab monotherapy permanent discontinuation is required.

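### The protocol leaves unclear whether a controlled Grade 4 adrenal insufficiency is a mandatory stop or may continue with Medical Monitor approval

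*Protocol*

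**What the plan says.** Three places in the protocol bear on the point.

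- **Section 8.1.1, Grade 3 items.** The endocrinopathy sub-item begins "Grade 3 drug-related endocrinopathies, adequately controlled with only physiologic hormone replacement do not require discontinuation". Its next sentence reads "Adrenal insufficiency requires discontinuation regardless of control with hormone replacement". That sentence names no grade itself but sits under the Grade 3 heading.
- **Section 8.1.1, Grade 4 items.** Any Grade 4 drug-related event stops treatment, "except for the following events which do not require discontinuation". One listed exception is "Grade 4 drug-related endocrinopathy adverse events, such as, hyper- or hypothyroidism, or glucose intolerance, which resolve or are adequately controlled with physiologic hormone replacement". The accepted replacements include corticosteroids, and continuing is possible only once the Medical Monitor has discussed the case and approved it. The named examples are thyroid and glucose events. Adrenal insufficiency is neither named nor excluded.
- **Section 8.1.2, resuming treatment.** One bullet says "Participants with drug-related endocrinopathies adequately controlled with only physiologic hormone replacement may resume treatment after consultation with the BMS Medical Monitor". The next repeats the adrenal stop sentence from 8.1.1, standing alone and without a grade.

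Section 9.2.1.1 lists adrenal insufficiency among the endocrine immune-mediated events. The SAP contains no stopping rule that would settle the scope.

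**The concern.** A permanent-discontinuation rule should give one answer for one patient. Here a participant with a drug-related Grade 4 adrenal insufficiency, adequately controlled on hormone replacement, meets the wording of a provision that may allow continuation with approval. The same participant meets the wording of a sentence that requires a stop whether or not replacement controls the event. Two sites, or two Medical Monitors, could read the text in good faith and act differently.

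What is at stake is first the participant's safety and continued exposure to study drug. There is a secondary effect on the data: the date of last dose sets the 100-day window in which further immune-mediated events count (Protocol 9.2.1.1; SAP 4.1), and it enters the exposure summaries (SAP 7.4.1).

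**Working it through.** No arithmetic applies, because the point rests on no rate, sample size or error level. The check is to ask whether the Grade 4 exception reaches adrenal insufficiency, and then to follow each reading of the stop sentence.

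**Step 1: can the Grade 4 exception reach adrenal insufficiency?** Three features of the text allow it.
- It covers endocrinopathies through an open list of examples, and Section 9.2.1.1 classes adrenal insufficiency as endocrine.
- It counts corticosteroids as physiologic hormone replacement, although its named examples are thyroid and glucose events. Elsewhere the protocol ties replacement steroids to the adrenal axis: Section 6.2 says "adrenal replacement steroid doses > 10 mg daily prednisone equivalents are permitted in the absence of active autoimmune disease".
- It has no adrenal exclusion, although the Grade 3 item in the same section and the resumption bullets in 8.1.2 each have one.

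This is an inference from the wording. The exception does not mention adrenal insufficiency.

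**Step 2: follow the two readings for a drug-related adrenal insufficiency controlled on replacement.**

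| | Reading A: stop sentence in 8.1.1 is Grade 3 only | Reading B: stop sentence applies at every grade |
|---|---|---|
| Grade 3 | Stop | Stop |
| Grade 4 under 8.1.1 | May continue with Medical Monitor approval | Stop |
| 8.1.2 adrenal bullet (no grade) | Stop, which conflicts with the Grade 4 row | Stop, consistent |
| What is left unresolved | The more severe event has the more permissive rule, and 8.1.2 disagrees with 8.1.1 | The Grade 4 exception has no matching exclusion, and its mention of corticosteroids is unexplained |

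**Step 3: does the text choose between them?** It does not. The layout of 8.1.1 favours A, because the sentence sits inside a Grade 3 sub-item and Grade 4 has its own rule and its own exceptions. The ungraded bullet in 8.1.2 favours B. The list of mandatory reasons in Section 8.1 points to 8.1.1 for further criteria, whereas the clearest ungraded statement is in 8.1.2, which concerns resumption.

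**Step 4: does the approval step settle it?** It prevents a site from using the exception alone. It does not tell the Medical Monitor whether adrenal insufficiency is within the exception. Under Reading B, approving continuation would depart from a mandatory rule, and Section 9 does not allow protocol waivers.

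**Step 5: effect on the primary endpoint.** Any participant at issue already has a Grade 4 adrenal event, which counts as an immune-mediated event without regard to immune-modulating medication (Protocol 9.2.1.1; SAP 4.1). If the other parts of the definition are met, that participant is already in the numerator of the high-grade incidence. Continuing or stopping can affect only later events and exposure.

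**The case against.** The strongest reply is that a specific rule governs a general one. The adrenal sentence names no grade in either place and overrides replacement control in terms; the Grade 4 exception is general, never names adrenal insufficiency, and is permissive and subject to approval. Section 8.1.2 uses the same structure: a general endocrinopathy allowance followed at once by the adrenal exclusion. On that view adrenal insufficiency stops at every grade and the passages are compatible. This is a natural reading, and it rules out calling the text an express contradiction. It does not show that the protocol adopts it: the Grade 4 exception is the one place where the exclusion is missing, and the layout of 8.1.1 points the other way.

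A reader might infer more than the documents support.
- *That the protocol inverts severity outright.* This holds only under Reading A.
- *That Grade 2 adrenal insufficiency is also in conflict.* Silence on that grade in 8.1.1 is compatible with an ungraded rule in 8.1.2.
- *That participants who enter on adrenal replacement under 6.2 meet the stop rule at baseline.* The bullets in 8.1.2 qualify a lead-in about drug-related adverse events, and Appendix 9 defines an adverse event as something new or a worsening. Stable pre-existing disease is neither.
- *That hypophysitis with secondary adrenal insufficiency is handled inconsistently.* The endocrine algorithm assigned to Appendix 8 is not reproduced in the text available, so this cannot be checked.
- *That coding would be driven by the treatment decision and distort the category counts.* Nothing in the documents shows this.

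**Conclusion.** The point holds as an unresolved inconsistency of scope. For a drug-related Grade 4 adrenal insufficiency controlled on replacement, Sections 8.1.1 and 8.1.2 support both a mandatory stop and continuation with approval, and the text does not say which governs. Neither reading leaves the wording clean. The conclusion assumes that the open list in the Grade 4 exception can include an event which the protocol itself classes as endocrine.

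The affected group is confined to Grade 4 cases. Their number cannot be derived, since the documents give no adrenal event rate, and it is probably small. The planned sample size and confidence-interval precision are untouched, and the headline incidence of high-grade immune-mediated events is not shown to move. The reason to act is participant safety under a permanent-stop rule.

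**What to change.** Reconcile the Grade 3 endocrinopathy item and the Grade 4 exception in Section 8.1.1 with the adrenal bullet in Section 8.1.2. The revised text should state:

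1. the grade or grades to which the adrenal insufficiency sentence applies, in the same words in both sections;
2. whether the Grade 4 endocrinopathy exception includes or excludes adrenal insufficiency.

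The sponsor's clinical team decides which rule holds; this review takes no position. How hypophysitis with secondary adrenal insufficiency is classed could be clarified in the same edit, although no contradiction has been shown there. The cost is a few lines of protocol wording, with no change to the sample size, data collection or the SAP analyses.

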8.1.2 Criteria to Resume Treatment

Missed doses of nivolumab and/or ipilimumab should be administered as soon as the participant meets criteria to resume treatment. If a dose has been missed, the participant should not wait until the next scheduled dosing date.

Participants may resume treatment with study drug when the drug-related AE(s) resolve to Grade ≤ 1 or baseline value, with the following exceptions:

- Participants may resume treatment in the presence of Grade 2 fatigue
- Participants who have not experienced a Grade 3 drug-related skin AE may resume treatment in the presence of Grade 2 skin toxicity
- For participants with Grade 2 AST, ALT and/or Total Bilirubin Abnormalities, dosing may resume when laboratory values return to baseline and management with corticosteroids, if needed, is complete.
- Participants with combined Grade 2 AST/ALT AND total bilirubin values meeting discontinuation parameters ([Section 8.1.1](#)) should have treatment permanently discontinued.
- Drug-related pulmonary toxicity, diarrhea or colitis must have resolved to baseline before treatment is resumed. Participants with persistent Grade 1 pneumonitis after completion of a steroid taper over at least 1 month may be eligible for retreatment if discussed with and approved by BMS Medical Monitor.
- Participants with drug-related endocrinopathies adequately controlled with only physiologic hormone replacement may resume treatment after consultation with the BMS Medical Monitor.
- Adrenal insufficiency requires discontinuation regardless of control with hormone replacement.

If treatment is delayed > 8weeks for Cohorts 2 through 4, or >10 weeks for Cohort 1, the participant must be permanently discontinued from study therapy, except as specified in [Section 8.1.1](#).

For participants in Cohort 1, during Cycles 1 and 2, both nivolumab and ipilimumab must be resumed on the same day. For participants in Cohort 2 to 4, all four doses of nivolumab combined with ipilimumab must be given prior to beginning nivolumab monotherapy (Cycle 3 and beyond). Participants in any cohort, who discontinue combination therapy early due to an adverse event, may be eligible to receive nivolumab monotherapy (480 mg every 4 weeks), contingent upon discussion with, and approval by the Medical Monitor.

If the participant is unable to receive either combination therapy or nivolumab monotherapy permanent discontinuation is required.

8.1.3 Post-Study Treatment Study Follow-up

BMS may request that survival data be collected on all treated participants outside of the protocol defined window (Schedule of Activities, [Section 2](#)). At the time of this request, each participant will be contacted to determine their survival status unless the participant has withdrawn consent for all contacts or is lost to follow-up.

8.2 Discontinuation from the Study

Participants who request to discontinue study treatment will remain in the study and must continue to be followed for protocol specified follow-up procedures. The only exception to this is when a participant specifically withdraws consent for any further contact with him/her or persons previously authorized by participant to provide this information.

- Participants should notify the investigator of the decision to withdraw consent from future follow-up **in writing**, whenever possible.
- The withdrawal of consent should be explained in detail in the medical records by the investigator, as to whether the withdrawal is from further treatment with study treatment only or also from study procedures and/or post treatment study follow-up, and entered on the appropriate CRF page.
- In the event that vital status (whether the participant is alive or dead) is being measured, publicly available information should be used to determine vital status only as appropriately directed in accordance with local law.
- If the participant withdraws consent for disclosure of future information, the sponsor may retain and continue to use any data collected before such a withdrawal of consent.

8.3 Lost to Follow-Up

- All reasonable efforts must be made to locate participants to determine and report their ongoing status. This includes follow-up with persons authorized by the participant.
- Lost to follow-up is defined by the inability to reach the participant after a minimum of **three** documented phone calls, faxes, or emails as well as lack of response by participant to one registered mail letter. All attempts should be documented in the participant's medical records.

- If it is determined that the participant has died, the site will use permissible local methods to obtain date and cause of death.
- If investigator's use of third-party representative to assist in the follow-up portion of the study has been included in the participant's informed consent, then the investigator may use a Sponsor retained third-party representative to assist site staff with obtaining participant's contact information or other public vital status data necessary to complete the follow-up portion of the study.
- The site staff and representative will consult publicly available sources, such as public health registries and databases, in order to obtain updated contact information.
- If after all attempts, the participant remains lost to follow-up, then the last known alive date as determined by the investigator should be reported and documented in the participant's medical records.

9 STUDY ASSESSMENTS AND PROCEDURES

- Study procedures and timing are summarized in the Schedule of Activities.
- Protocol waivers or exemptions are not allowed.
- All immediate safety concerns must be discussed with the Sponsor immediately upon occurrence or awareness to determine if the participant should continue or discontinue treatment.
- Adherence to the study design requirements, including those specified in the Schedule of Activities, is essential and required for study conduct.
- All screening evaluations must be completed and reviewed to confirm that potential participants meet all eligibility criteria before treatment allocation. The investigator will maintain a screening log to record details of all participants screened and to confirm eligibility or record reasons for screening failure, as applicable.
- Procedures conducted as part of the participant's routine clinical management (e.g., blood count) and obtained before signing of informed consent may be utilized for screening or baseline purposes provided the procedure meets the protocol-defined criteria and has been performed within the timeframe defined in the Schedule of Activities.

